This study protocol reflects the topics defined in annex A (clinical investigation plan) of ISO 14155:2020. Topics 1.1 to 1.3 are represented on the cover page, thus, numbering starts with topic 1.4 of annex A as 1.1 of this study protocol. Some headlines of annex A have been modified to better represent the needs of this non-interventional, observational study, e.g. 1.4 (here 1.1) which is renamed to "Steering Committee". A list of principal investigators, investigation sites, and institutions according to 1.4 of annex A is given in a stand-alone document referred to in Annex 1 of this study protocol.

Throughout this study protocol the term "study" is used as umbrella term for any systematic clinical investigation involving one or more human subjects (e.g. observational clinical investigations) whereas "trial" means any study which is interventional (e.g. by means of randomisation) and "investigation" is being used as regulatory term for any study undertaken to assess the safety or performance of a dedicated investigational product. Consequently, the term "study" will also be used in compound words in the sense described above, e.g. "study site" instead of "investigation site" or "study protocol" instead of "investigation plan".

1.1 Steering Committee (SC)

An independent SC is responsible for scientific and medical advice of the sponsor including continuous overview of the study to assure reliability of data collected and analysed within this non-interventional, observational study. A corresponding charter defines duties and responsibilities of the SC. A list of SC members is provided in a separate document.

1.2 Clinical Event Committee (CEC)

The CEC will centrally adjudicate serious adverse events (SAEs) and adverse events (AEs) of special interest based on coded (pseudonymized) copies of corresponding medical files to assess if it fulfils criteria for defect treatment complication or being related to defect treatment. In addition, because hospitalisation decisions might be subject to local practices, social considerations, bed availability, and so on, all hospitalisations will be reviewed to assess the reason and appropriateness of each hospitalisation, i.e. whether it is "for therapy of index defect".

A corresponding charter defines duties and responsibilities of the CEC. A list of CEC members is provided in a separate document.

1.3 Overall synopsis of the clinical study

TITLE	Suprasorb [®] CNP endo used for negative pressure therapy in the oesopha- gus and rectum to support defect and wound healing	
CHIEF INVESTIGATOR	[name]. med. [name], Rheine	
ACRONYM	Velox Study	
SPONSOR	Lohmann & Rauscher GmbH & Co. KG [name]	
BACKGROUND AND RATIONALE	Anastomotic insufficiencies and oesophageal perforations are life-threaten- ing, severe complications of the upper gastrointestinal (GI) surgery. The re- ported incidence of anastomotic leaks overall is between 5% and 25%. De- pending on the position and dimensions of the leaks, they are associated with a mortality of up to 60% [28]. Therapy of patients who experience sympto- matic intrathoracic anastomotic leaks is usually difficult and carries a high risk of severe secondary complications. Depending on the severity of the anasto- motic leakage, the time interval after primary surgery, the general condition of the patient and the anastomotic location, several treatment strategies are available, such as conservative, endoscopic or surgical treatment. Conserva- tive treatment approach includes strict nil per oral, drainage and i.v. antibiot- ics. Surgical treatment options span from the re-execution of the anastomosis with augmentation of the anastomotic area by vital tissue (e.g. muscle flap, omental flap), to complete surgical deviation by taking down the oesophageal conduit and creation of a cervical stoma. Endoscopic methods include injec- tion of fibrin glue and clip administration, introduction of self-expanding metal or plastic stents and endoluminal vacuum therapy.	
	Colorectal anastomotic leakage (CAL) also remains a frequent and danger- ous complication after gastrointestinal surgery, occurring in 4-33% of patients and contributing to one third of postoperative mortality. An anastomotic defect causes leakage of colonic content into the abdominal or pelvic cavity, leading to peritonitis, abscess formation or sepsis. CAL substantially (by 1-2 weeks) prolongs hospital stay and increases medical costs by as much as US\$24,000 within the first period of hospitalisation, thereby approximately tripling the expenditure in comparison to that of a normal recovery. Moreover, CAL is identified as a risk factor for local recurrence of colorectal cancer and is reported to reduce long-term cancer specific survival.	
	The type of intervention strongly depends on the severity of CAL, which is hard to determine, and therefore the choice of intervention for a suspicious leakage is quite complex with very limited evidence-based strategy available at present. Colorectal surgeons use various methods, i.a. conservative fol- low-up, adhesive materials (e.g. cyanoacrylate), abscess drainage, open pel- vic lavage, construction of an entirely new anastomosis, and endoscopic or surgical interventions, such as diverting or ending the stoma and transanas- tomotic continuous drainage system with negative pressure.	
	Though a number of studies and case reports have demonstrated promising results regarding efficacy of EVT in treatment of both upper and lower GI tract	

	perforations and anastomotic insufficiencies, and, potentially, even better safety profile of this treatment in comparison with other conventional treat- ment methods, the amount of data is still relatively small and additional data collection and analysis is necessary.	
STUDY OBJECTIVE(S)	To assess in a routine clinical care setting the performance of Suprasorb [®] CNP endo regarding wound healing in patients with oesophagus and rectum defects of different aetiologies.	
STUDY DESIGN	This PMCF study designed as non-interventional, observational, prospective, multicentre study in a routine clinical care setting using a marketed medical device in line with the corresponding IFU in the intended patient population.	
STUDY POPULATION	Inclusion criteria:	
Medical condition/	I1. ≥ 18 years of age	
main selection criteria	 Acute transmural defects, injuries and wounds in oesophagus or rec- tum, including perforations (iatrogenic or spontaneous) and anastomotic insufficiencies (Index defect) 	
	I3. Indication of treatment with Suprasorb [®] CNP endo system according to IFU and medical guidelines	
	14. Signed informed consent for usage of data	
	Exclusion criteria:	
	E1. Pre-existing coagulation disorders with increased risk of bleeding	
	E2. Defects involving the bronchial system (bronchus/trachea/pulmo)	
	E3. Any foreseeable deviation from IFU of Suprasorb [®] CNP endo	
	E4. Known intolerance or allergy to one or more components of Suprasorb [®] CNP endo	
Number of subjects	About 110 adult female and male patients with acute defects, injuries and wounds in the oesophagus or rectum and an indication of treatment with Suprasorb [®] CNP endo system according to IFU and medical guidelines.	
Expected number of sites and countries	About 10 study sites in Germany, which are trained for the use of Suprasorb [®] CNP endo system treatment in routine clinical care, will screen eligible patients.	
INVESTIGATIONAL INTERVENTIONS	The study protocol does not define specific study procedures for patients en- rolled. Therapies and procedures during the course of this study will be per- formed according to the decision of the treating physician based on current applicable medical guidelines and on local policy in clinical routine care. This includes the prescription and the use of the device of interest and possible measures at enrolment and in follow-up. All devices will be used according to the corresponding IFU, only. The only study-specific obligation within this observational study is to document pre-defined medical and procedural data if available in routine clinical care in the electronic CRF (eCRF) at a level of data quality following international standards on clinical studies.	

	Primary endpoint		
OUTCOME PARAMETERS	Time period in days from index use of Suprasorb [®] CNP endo to release for oral food intake (in upper GI tract use) or endoscopic release for stoma relocation (in lower GI tract use).		
	Secondary endpoints		
	1. Number of SAEs related to defect treatment within total observation period.		
	2. Number of nights in hospital for therapy of index defect.		
	 Number of nights at the ICU during hospital stay for therapy of index defect. 		
ASSESSMENT	 Screening and baseline/enrolment visit (day 1). 		
SCHEDULEs	 Treatment of the index defect 		
	 Follow-up (FU) visits 		
STATISTICAL CONSIDERATIONS	In this observational study the time period from index therapy to release for oral food intake (in upper GI tract use) or endoscopic release for stoma relocation (in lower GI tract use) will be compared to published historic controls. For this, the time period is compared to published data of other EVAC and conventionally managed therapy, especially data from Wasmann et al. [29]. In addition, after half of the patients with complete follow-up, an interim analysis will be performed and sample size will be recalculated. It is expected that until then the results of a randomized clinical trial comparing an EVAC therapy to standard minimally invasive oesophagectomy (refer to NCT04162860 and [22]) will be available for adaptation of assumed confidence intervals and sample size (see 6.3.7). The hypothesis of superiority against conventionally managed therapy will be tested confirmatory. Data from all study sites will be pooled for analysis. Standard statistical methods will be used to analyse all data. Continuous variables will be summarized using the number of observations, mean, median, standard deviation, minimum and maximum values. Categorical variables will be summarized using the number of observations and percentages.		
DURATION OF STUDY	Total study duration:		
PERIODS	 Enrolment period: about 24 months. 		
	 Follow-up period of last patient enrolled: about 3 months. 		
	Total study period: about 27 months.		
	Individual study duration:		
	 Expected median follow-up period: about 3 months per patient. 		

2. Identification and description of the investigational device(s)

This is a non-interventional, purely observational study using only marketed medical devices in line with the approved Instruction For Use (IFU) in the intended patient population. The investigational device is Suprasorb[®] CNP endo, used for EVAC, an endoscopic vacuum assisted therapy or endoluminal negative pressure wound therapy, assessed as class IIb (EU Quality Management System Certificate (MDR) G10 045286 0079 Rev.01) and class I medical devices (please refer to **Medicinal Product Marketing Authorisation No.**)

The Suprasorb[®] CNP endo therapy unit is used in combination with Suprasorb[®] CNP endo Kits to create, maintain, and control negative pressure and to drain body fluids in the upper and lower GI tract. EVAC can be used as intraluminal or intracavitary treatment of defects of the upper and lower GI tract. Negative pressure wound therapy drainage properties are achieved by a connection to the therapy unit with exudate canister which continuously removes secretions from wounds. The devices are available as disposable accessories for the use with the Suprasorb[®] CNP endo therapy unit in 4 different Kitpacks: Suprasorb[®] CNP endo Kit Oral, Suprasorb[®] CNP endo Kit Oral N, Suprasorb[®] CNP endo Kit Rectal and Suprasorb[®] CNP endo Kit AddOn. A detailed description is provided in the approved IFU.

The investigational devices will be used in routine clinical care based on the decision of the treating physician in line with IFU, medical guidelines and local policy.

3. Justification for the design of the clinical study

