In the retrospective analysis by Brangewitz et al. [6], comparing EVT versus stent management (self-expanding metal (SEMS) or plastic stents (SEPS)), data of 39 patients who were treated with SEMS or SEPS and 32 patients who were treated with EVT for intrathoracic leakage were analysed. Successful wound closure was independently associated with EVT (hazard ratio 2.997, 95% confidence interval [95%CI] 1.568–5.729; P=0.001). The overall closure rate was significantly higher in the EVT group (84.4%) compared with the SEMS/SEPS group (53.8%). No difference was found for hospitalisation and hospital mortality. Significantly more strictures were observed in the stent group (28.2% vs. 9.4% with EVT, P<0.05). Complications in the stent group constituted: stent dislocation (n=6), anastomotic stricture (n=11), severe bleed at the upper end of the stent followed by immediate surgical revision (n=1), oesophageal necrosis with fatal outcome (n=1), self-limiting bleeding after stent-removal (n=2), ulcers after stent removal, not requiring specific therapy (n=5). Complications in the EVT group constituted: sponge dislocation (n=5), bleeding after sponge removal (n=1), significant mucosal tear proximal to the anastomosis during sponge removal (n=1), bronchooesophageal fistual with later required surgery (n=1), anastomotic stricture (n=3).

Heits et al. [8] analysed data of 10 patients, treated by EVT for oesophageal perforations, located in the cervical (n=3) and thoracic (n=7) oesophagus. Complete healing of the wound was achieved in 9 cases. One patient has died (failure of the cardiovascular system caused by a known heart insufficiency). EVT-associated complications (mediastinal emphysema) occurred in 7 patients.

Bludau et al. [4] summarized the experience of EVT for patients with oesophageal leakages (n=14). For 6 of 14 patients, EVT was combined with a placement of self-expanding metal stents. Complete closure of the

oesophageal defect was achieved in 12 cases. Two patients died due to prolonged sepsis before EVT could be completed. In two cases, oesophageal stenosis was diagnosed, which was treated successfully by one-time pneumatic dilation. No other complications related to the EVT were observed.

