5.4 Risks and anticipated adverse device effects that are to be assessed

The investigational device is a marketed, CE-certified product, which will be used within its intendent purpose. Rate of defect treatment complications (during index defect treatment and in follow-up treatments) and rate of SAEs related to defect treatment will be assessed. The term "defect treatment related" represents not only device-related but in total procedure-related AEs of special interest and SAEs. Non-serious AEs which are not classified as "of special interest" will not be assessed.

6. Design of the clinical study

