6.4.4 Treatment of the index defect

The decision of treatment of the index defect lies with the treating physician in routine clinical care. Indication as well as initiation of treatment should follow applicable medical guidelines, local clinical care policy and the IFUs of the devices used.

Initiation of treatment might start as routine clinical care procedure before enrolment into the study (i.e. informed consent of the patient) but data can be entered into the e-CRF after signed informed consent is available (i.e. after enrolment), only.

- Primary EV therapy is defined as the utilisation of EVT as first-line therapy for perforation or leak.
- **Rescue EV therapy** is defined as EVT placement following failure of definitive surgical repair for a perforation or leak.
- **Defect closure following EVT placement** is defined as 1) no evidence of continued leak under direct endoscopic visualization and 2) a negative oesophagram following discontinuation of EVT therapy.

Data regarding index defect, related therapy and outcome following EVT placement will be documented in the e-CRF at the Index-treatment visit.

The following data items will be documented of each participating patient at the index-treatment visit:

- Data of index treatment and related therapy (defect size, type and location of perforation, pre-existing pathology, ASA-classification, Perforation Severity Score (PSS), primary or rescue EVT application, type of endo-sponge placement, type of surgical repair, time to placement of EVT following diagnosis, number of EVT changes, number of days between EVT changes, total length of EVT therapy, relevant laboratory parameters)
- Outcome of index treatment (including 30-day mortality, closure interventions following treatment of index defect, hospital length of stay (LOS), ICU LOS, EVT therapy-specific findings (e.g. migration, dislodgement, erosion), time to oral diet initiation / endoscopic release for stoma relocation following successful defect closure).

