14.3 Recording and reporting of reportable events

The following events are considered reportable events in accordance with MDR Art. 80(2):

- any SAE that has a causal relationship with the investigational device, the comparator or the investigation
 procedure or where such causal relationship is reasonably possible;
- any DD that might have led to a SAE if appropriate action had not been taken, intervention had not occurred, or circumstances had been less fortunate;
- any new findings in relation to any event referred to in the points above.

Since this study is observational, no investigational medical product will be used but all therapies and procedures represent routine clinical care in line with applicable medical guidelines, market authorisations and corresponding IFUs. Thus, causal relationships of events to an investigational device or procedure will not be assumed. However, irrespective of this study, treating physicians have to report AEs related to medical devices or therapies to the corresponding manufacturers of devices concerned. Reporting duties of manufacturers of devices used within this observational study have to follow routine procedures relevant for marketed medical devices.

Information on all SAEs which occurred after start of index treatment, whether related or not related to index treatment, must be collected. The investigator should specify and report in the e-CRF the nature of the sign or symptom leading to the SAE, the date of onset of the sign or symptom, the date of resolution of the specific event (not of the underlying disease), the intensity, interventions performed (if any), the relationship to index treatment, and the outcome.

All SAEs must be reported expeditiously by the investigator to the sponsor through the SAE section of the e-CRF within 24 hours of becoming aware of the event. A SAE form within the e-CRF should be completed for any event where doubt exists regarding its status of seriousness. As a minimum, the investigator has to fill out the following items in the internet-based SAE form within 24 hours of becoming aware of the event:

- Type of event
- Description
- Date of onset
- Criteria for seriousness

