14.3.2 Definition of Causality

The sponsor and the investigators will use the following definitions to assess the relationship of SAEs to the index therapy (devices used and procedure itself).

Not related

Relationship to index therapy can be excluded when:

- the event has no temporal relationship with the use of the devices or the procedures;
- the SAE does not follow a known response pattern to the index therapy (if the response pattern is previously known) and is biologically implausible;
- the discontinuation of the index therapy or the reduction of the level of activation/exposure when clinically feasible - and reintroduction of its use (or increase of the level of activation/exposure), do not impact on the SAE;
- the event involves a body-site or an organ that cannot be affected by the index therapy;
- the SAE can be attributed to another cause (e.g. an underlying or concurrent illness/ clinical condition, an effect of other devices, drugs, treatments or other risk factors).

In order to establish the non-relatedness, not all the criteria listed above might be met at the same time, depending on the type of device/procedures and the SAE.

Possible

The relationship with the index therapy is weak but cannot be ruled out completely. Alternative causes are also possible (e.g. an underlying or concurrent illness/ clinical condition or/and an effect of other devices, drugs or treatments). Cases where relatedness cannot be assessed, or no information has been obtained should also be classified as possible.

Probable

The relationship with the index therapy seems relevant and/or the event cannot be reasonably explained by another cause.

Causal relationship

The SAE is associated with the index therapy beyond reasonable doubt when:

- the event is a known side effect of the index therapy or of similar devices and procedures;
- the event has a temporal relationship with the index therapy;
- the event involves a body-site or organ that
 - the index therapy is applied to;
 - the index therapy has an effect on;
- the SAE follows a known response pattern to the index therapy (if the response pattern is previously known);
- the discontinuation of the index therapy (or reduction of the level of activation/exposure) and reintroduction
 of its use (or increase of the level of activation/exposure), impact on the SAE (when clinically feasible);

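### The only listed safety endpoint counts treatment-related SAEs, so deaths attributed to the underlying illness can enter no safety endpoint, although they are documented for enrolled patients

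*Protocol*

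**What the plan says.** Sections 1.3 and 6.1.3.2 list one primary and three secondary endpoints. The primary endpoint is time to release for oral food or stoma relocation. Two of the secondary endpoints count nights in hospital and in the ICU. The only safety endpoint is "Number of SAEs related to defect treatment within total observation period".

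Section 5.4 explains that the term related to defect treatment "represents not only device-related but in total procedure-related AEs of special interest and SAEs". This is wider than device-related but still not all-cause. The same section states: "Rate of defect treatment complications (during index defect treatment and in follow-up treatments) and rate of SAEs related to defect treatment will be assessed". Complications of treatment are thus also assessed, but they are not a listed endpoint, and they too depend on attribution to treatment.

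Under 14.3.2, one ground for rating an event not related is that "the SAE can be attributed to another cause (e.g. an underlying or concurrent illness/ clinical condition", among other causes, explains it.

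Collection is wider than the endpoint. Section 14.3 requires: "Information on all SAEs which occurred after start of index treatment, whether related or not related to index treatment, must be collected". Death is an SAE criterion in 14.1, and 6.4.4 records "Outcome of index treatment (including 30-day mortality, closure interventions following treatment of index defect" and further outcome items.

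**The concern.** Secondary objective 1 (5.2.2) is adequate safety of the device. Section 4.1 names mediastinitis, peritonitis and fatal sepsis as the danger these patients face, and 3.1 cites mortality of up to 60% for upper-GI leaks. A death from that hazard is the kind of event that can be put down to the underlying illness. Section 3.2 gives an example from a 14-patient series: "Two patients died due to prolonged sepsis before EVT could be completed". Such a death might be rated not related, possible, or a treatment complication. The protocol does not say which, nor which grades enter the endpoint.

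The other endpoints do not make up for this. A patient who dies before release appears in the primary endpoint only as someone without an event. An early death shortens the hospital and ICU night counts, which can look favourable. Section 6.2 defines no control group, so the relatedness judgement has nothing to be calibrated against.

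A related-only count also cannot be set beside the mortality figures that 3.2 quotes for vacuum therapy, surgery and stents, because those are not filtered by relatedness.

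**Working it through.** **1. The protocol's own mortality figures reproduce.** In the 62-patient comparison of treatments in 3.2, (2 + 9 + 5 + 0)/62 = 25.8%, stated as 26%. Its vacuum-therapy group is 2/17 = 11.8%, stated as 12%. In the 55-patient series, 4/55 = 7.27%, stated as 7.2%.

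**2. Deaths under vacuum therapy in the 3.2 series that give a count.**

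| Series (3.2) | Patients | Deaths | Cause as the protocol reports it |
|---|---|---|---|
| Oesophageal defects, mixed | 10 | 1 | colitis |
| Oesophageal perforations | 10 | 1 | cardiovascular failure |
| Oesophageal leakages | 14 | 2 | sepsis before therapy was completed |
| Upper-GI leaks and perforations | 6 | 1 | unrelated complication |
| Oesophageal insufficiencies | 52 | 2 | procedural haemorrhage |
| Leak after oesophageal resection | 55 | 4 | 3 organ failure, ARDS or urosepsis; 1 not given |
| Vacuum-therapy group of the 62-patient comparison | 17 | 2 | not given |
| **Total** | **164** | **13** | 2 procedural, 2 sepsis, 6 other, 3 not given |

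Rate: 13/164 = 7.9%.

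**3. Share falling outside a related-only count.**
- If only the stated procedural deaths count as related: 2/13 = 15% inside, 11/13 = 85% outside.
- If sepsis and unknown causes also count as related: (2 + 2 + 3)/13 = 7/13 = 54% inside, 6/13 = 46% outside.
- Among the 10 deaths with a stated cause: 8/10 outside, or 6/10 if the septic deaths count as related.

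These are results under two stated rules, not limits. Liberal use of *possible* could bring the share below 46%.

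**4. Projection to this study.** Section 6.3.7 plans 110 patients and 6.3 says upper and lower GI will be about equally balanced, so about 55 each. All seven series are upper GI. No lower-GI vacuum series cited in 3.2 gives an all-cause death count, so the lower-GI rate is an assumption, shown at two values.

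| Lower-GI mortality assumed | Expected deaths | Outside at 46% | Outside at 85% |
|---|---|---|---|
| Zero | 55 × 0.0793 = 4.4 | 2.0 | 3.7 |
| 7.9%, as in upper GI | 110 × 0.0793 = 8.7 | 4.0 | 7.4 |

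Roughly 2 to 7 deaths would not be counted by the safety endpoint.

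**5. Direction of error.** The pool keeps only series that report deaths, which pushes the rate up. Adding the two small pilot series in 3.2 (5 and 8 patients) in which no death is mentioned gives 13/177 = 7.3%. Enrolled patients must also have lived long enough to consent, so the number of deaths seen in the study should be lower still.

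**6. Precision of an all-cause figure.** Exact 95% intervals: 9/110 = 8.2% (3.8% to 15.0%); 4/55 = 7.3% (2.0% to 17.6%). These are wide, but they are informative against the cited 42% and 50% for stent and surgery.

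**The case against.** **Septic deaths are not excluded by rule.** A reader might infer that most deaths, and all deaths from an uncontrolled leak, drop out. The text does not support this. Relatedness covers the whole procedure (5.4). The grade *possible* takes weak links and cases that cannot be assessed (14.3.2). The committee also adjudicates treatment complications (1.2, 14.1), and peritonitis, mediastinitis and abscess as a symptom of treatment are events of special interest. This stands: the fault is that the classification is left open. That most deaths fall outside is likely on the cited series but not certain.

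**Not every death is recorded.** A reader might infer from 14.3 that the data are complete. Signed consent is an inclusion criterion (6.3.1), is expected after treatment in most patients (6.1.6), and must precede any e-CRF entry (section 13). Patients who die before consenting leave only age, sex and indication in a site log that is not processed centrally (6.1.2). This also stands, and it shapes the fix, because 30-day mortality among patients who lived to consent is biased low.

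**The number is borrowed from the wrong half of the population.** A single figure of about 9 deaths would treat upper-GI mortality as applying to everyone. This is correct, and is why a range is given and called an illustration.

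**The analysis may cover mortality anyway.** Section 7 says all data will be analysed, and a separate SAP may tabulate deaths. Nor does the protocol say that adequate safety will be concluded from this endpoint alone. Both are true, but a table does not change the endpoint list, and no other listed endpoint addresses safety.

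**All-cause death has no concurrent benchmark either.** This is fair. It can, however, be set beside the published mortality in 3.2, and counting it needs no causal judgement.

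**Conclusion.** The concern holds in a limited form. The safety objective has one listed endpoint. It is filtered by relatedness, the grades that count as related are not defined, and there is no control group. Deaths and SAEs attributed to the underlying illness can therefore enter no safety endpoint, although they are documented for enrolled patients.

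The illustrative size is 2 to 7 uncounted deaths in 110. It rests on three assumptions: 7.9% upper-GI mortality taken from series selected for reporting deaths, lower-GI mortality between zero and that value, and 46% to 85% of deaths judged not related. The design point does not depend on the exact figure. The documents do not support saying that most deaths will certainly be missed, that septic deaths are excluded by definition, or that every death among treated patients is captured. This should be changed; it does not affect the primary test.

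**What to change.** In 1.3 and 6.1.3.2:

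1. Add all-cause death at 30 days from index use and to end of observation, as percentages with exact 95% confidence intervals, overall and by upper and lower GI.
2. Add all SAEs regardless of relatedness, shown beside the committee-adjudicated related count.
3. State which causality grades count as related (for example possible, probable and causal) and how a death from an uncontrolled leak is to be classed.
4. Label the mortality figures as applying to consented patients and report the time from index use to consent. Add a delayed-entry analysis in which each patient is at risk only from the date of consent. Index-treatment and enrolment dates are both available for this.

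The cost is protocol and analysis wording plus a little more analysis. No new data item or procedure is needed for enrolled patients. The downside for the sponsor is a less favourable safety figure. Delayed entry corrects the survival-to-consent bias in the analysed risk time, but it cannot recover deaths that occurred before consent, and the report should say so.
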